15.2.2. Protocol Defined Schedule of Events for Q8W Arm in Main Study

| Procedure | Screening Visit ^a | Maintenance Phase | | | | | | | | | | | | | | | Extension Phase | | Withdrawal Assessments ^y | Long-Term Follow-up ^z | |
|--|------------------------------|---------------------------|--|------|---|----|----|----|----|----|----|----|----|----|----|----|-----------------|-----|-------------------------------------|----------------------------------|--|
| | | Day 1 | | Week | | | | | | | | | | | | | | | | | |
| | | Week 4A (Oral lead-in) | Week 4B (Oral lead-in ONLY) ^b | 8 | 9 | 16 | 24 | 32 | 40 | 41 | 48 | 56 | 64 | 72 | 80 | 88 | 96 | 100 | Q8W After Week 96 | 152 | |
| Written informed consent | X | | | | | | | | | | | | | | | | | | | | |
| Eligibility Verification (Inclusion/Exclusion Criteria) | X | | X ^c | | | | | | | | | | | | | | | | | | |
| Randomization | | X | | | | | | | | | | | | | | | | | | | |
| Demography | X | | | | | | | | | | | | | | | | | | | | |
| Medical History ^d | X | | | | | | | | | | | | | | | | | | | | |
| Cardiovascular risk assessment ^d | X | X | | | | | | | | | | | | | | | | | | | |
| Medication History/ Prior ART history | X | | | | | | | | | | | | | | | | | | | | |
| Syphilis serology + reflex Rapid Plasma Reagin (RPR) | X | X | | | | | | | | | | | | | | | | | | | |
| Symptom Directed Physical Exam and Medical Assessment ^e | X | X | X | X | X | X | X | X | X | X | X | X | X | X | X | X | X | X | X | X | |

| Procedure | Screening Visit ^a | Maintenance Phase | | | | | | | | | | | | | | | | | | Extension Phase | | Withdrawal Assessments ^y | Long-Term Follow-up ^z | |
|---|------------------------------|---------------------------|--|------|---|----|----|----|----|----|----|----|----|----|----|----|----|-----|----------------------|-----------------|---|-------------------------------------|----------------------------------|--|
| | | Day 1 | | Week | | | | | | | | | | | | | | | | | | | | |
| | | Week 4A (Oral lead-in) | Week 4B (Oral lead-in ONLY) ^b | 8 | 9 | 16 | 24 | 32 | 40 | 41 | 48 | 56 | 64 | 72 | 80 | 88 | 96 | 100 | Q8W After Week 96 | 152 | | | | |
| Weight, Height and BMI ^f | | X | | | | | | | | | X | | | | | | | | | | X | X | | |
| Vital Signs (BP, HR, Temperature) ^g | X | X | | | | | | | | | X | | | | | | | | | | X | X | | |
| 12-lead ECG ^h (triplicate at Day 1 pre-dose) | X | X | | | | | | | | | X | | | | | | | | | | X | X | | |
| CDC HIV-1 stage | X | X | | | | | | | | | | | | | | | | | | | | | | |
| HIV Associated Conditions | | X | X | X | X | X | X | X | X | X | X | X | X | X | X | X | X | X | X | X | X | X | | |
| AEs, SAEs, Concomitant Medications | X ⁱ | X | X | X | X | X | X | X | X | X | X | X | X | X | X | X | X | X | X | X | X | X | | |
| ISR Assessment for IM injection | | X | | X | X | X | X | X | X | X | X | X | X | X | X | X | X | X | X | X | X | X | | |
| Columbia Suicide Severity Rating Scale (eC-SSRS) ^j | X | X | | X | X | | X | X | X | X | | X | X | X | X | X | X | | | | | X | | |
| Clinical chemistry and Hematology | X | X | X | X | X | | X | X | X | X | | X | X | X | X | X | X | X | X | X | X | X | | |
| Pregnancy Testing ^k | S | U | S | U | S | | S | S | S | S | | S | S | S | S | S | S | S | S | S | S | S | | |

CONFIDENTIAL

207966

| Procedure | Screening Visit ^a | Maintenance Phase | | | | | | | | | | | | | | | | | | Extension Phase | | Withdrawal Assessments ^y | Long-Term Follow-up ^z | |
|---|------------------------------|---------------------------|--|------|---|----|----|----|----|----|----|----|----|----|----|----|----|-----|----------------------|-----------------|----------------|-------------------------------------|----------------------------------|--|
| | | Day 1 | | Week | | | | | | | | | | | | | | | | | | | | |
| | | Week 4A (Oral lead-in) | Week 4B (Oral lead-in ONLY) ^b | 8 | 9 | 16 | 24 | 32 | 40 | 41 | 48 | 56 | 64 | 72 | 80 | 88 | 96 | 100 | Q8W After Week 96 | 152 | | | | |
| HIV-1 RNA and sample for storage (S) ¹ | X | X | | X | X | | X | X | X | | X | X | X | X | X | X | S | X | X | | X | X | | |
| CD4+ cell count | X | X | | X | X | | X | X | X | | X | X | X | X | X | X | X | X | X | | X | X | | |
| CD8+ cell count | | X | | | | | X | | | | X | | | | | | X | | | X | X | | | |
| Urinalysis ^m | | X | X | | | | X | | | | X | | | | | | X | | | X | X | | | |
| Fasting Labs Glucose, Cholesterol (Total, HDL and LDL) and Triglycerides ⁿ | | | X | | | | | | | | X | | | | | | | | | X | X ^o | | | |
| Hepatitis B (HBsAg), Anti-HBc, and Anti-HBsAG, Hepatitis C (anti-HCV Ab) | X | | | | | | | | | | | | | | | | | | | | | | | |
| PT/PTT/INR | X | X | | | | | | | | | | | | | | | | | | | | | | |
| PBMCs ^p | | X | | | | | | | | X | | | | | | | X | | | X | X | | | |
| Genetics sample ^q | | X | | | | | | | | | | | | | | | | | | | | | | |

CONFIDENTIAL

207966

| Procedure | Screening Visit ^a | Maintenance Phase | | | | | | | | | | | | | | | | | | | Extension Phase | | Withdrawal Assessments ^y | Long-Term Follow-up ^z | | |
|--|------------------------------|---------------------------|--|------|---|----|----|----|----|----|----|----|----|----|----|----|----|-----|----------------------|-----|-----------------|---|-------------------------------------|----------------------------------|--|--|
| | | Day 1 | | Week | | | | | | | | | | | | | | | | | | | | | | |
| | | Week 4A (Oral lead-in) | Week 4B (Oral lead-in ONLY) ^b | 8 | 9 | 16 | 24 | 32 | 40 | 41 | 48 | 56 | 64 | 72 | 80 | 88 | 96 | 100 | Q8W After Week 96 | 152 | | | | | | |
| PK sampling when transitioning from SOC ^r (S)=Storage only | | | X | X | X | X | X | X | X | X | S | S | S | S | S | X | S | X | S | X | X | X | | | | |
| PK sampling when transitioning from CAB + RPV Q4W ^r (S)=Storage only | X | | | X | X | X | X | X | X | X | S | S | S | S | S | X | S | | X | X | X | X | | | | |
| Oral CAB and Oral RPV Dispensation ^s | X | X | | | | | | | | | | | | | | | | | | | | | | | | |
| IP accountability (Pill Counts) | | X | X | | | | | | | | | | | | | | | | | | | | | | | |
| IM treatment administration when transitioning from SOC ^t | | | X | X | | X | X | X | X | | X | X | X | X | X | X | X | X | X | X | X | X | | | | |

CONFIDENTIAL

207966

| Procedure | Screening Visit ^a | Maintenance Phase | | | | | | | | | | | | | | | | | | Extension Phase | | Withdrawal Assessment ^y | Long-Term Follow-up ^z | | |
|---|--|-------------------|------------------------|--|---|---|----|----|----|----|----|----------------|----|----|----|----|----|----|-----|-------------------|-----------------|------------------------------------|----------------------------------|--|--|
| | | Day 1 | Week | | | | | | | | | | | | | | | | | Q8W After Week 96 | 152 | | | | |
| | | | Week 4A (Oral lead-in) | Week 4B (Oral lead-in ONLY) ^b | 8 | 9 | 16 | 24 | 32 | 40 | 41 | 48 | 56 | 64 | 72 | 80 | 88 | 96 | 100 | | | | | | |
| IM treatment administration when transitioning from CAB + RPV Q4W | X | | | | X | | X | X | X | X | | X | X | X | X | X | X | X | | X | X | | | | |
| Patient Reported Outcomes ^u | | | | | | | | | | | | | | | | | | | | | | | | | |
| HAT-QoL (short-form) | | X | | | | | X | | | | | X | | | | | | | | | | X | | | |
| HIV TSQs | | X | | | | | | X | | | | X | | | | | | | | | | X | X | | |
| HIV TSQc ^v | | | | | | | | | | | | X | | | | | | | | | | | X | | |
| ACCEPT | | X | | | | | X | | | | | X | | | | | | | | | | X | X | | |
| Reason for Switch or Reason for continuation ^w | | X | | | | | | | | | | | | | | | | | | | | | | | |
| Preference Questionnaires | | | | | | | | | | | | X ^x | | | | | | | | | X ^{aa} | X | | | |
| PIN | | | | | X | | X | | | | | X | | | | | | | | | X | X | | | |
| | Safety Follow Up Visit: Conduct approximately 4 weeks after the last dose of IP. Required only if the participant has ongoing AEs or lab abnormalities at the last on-study visit. This visit may be conducted by telephone. | | | | | | | | | | | | | | | | | | | | | | | | |

- a. Participants may be rescreened once and will be assigned a new participant number. Participants transitioning from the 201585 (ATLAS) study must reach ATLAS Week 48 (at minimum) prior to initiating Screening procedures for ATLAS-2M and must reach ATLAS Week 52 (at minimum) prior to randomization in ATLAS-2M.
- b. Visits Weeks 4A and 4B are part of the CAB + RPV Oral Lead-in period and are required only for participants transitioning from current SOC to CAB LA + RPV LA.
- c. Confirmation of eligibility to continue the Maintenance Phase, and eligibility to enter the Extension Phase.

- d. Collect full routine medical history plus (report at Baseline visit): HIV risk factors (may be collected at a later study visit), cardiovascular risk factors (assessments include smoking status and history, family history of cardiac events), recent [\leq 6 months] illicit drug use, intravenous drug use, gastrointestinal disease, metabolic, psychiatric, renal, bone, and neurologic disorders.
- e. Physical exams should be conducted as part of normal routine clinical care. Medical assessments include any decisions the study staff must make for participants management and/or care of participant.
- f. Height collected at Baseline Day 1 only.
- g. Measure vital signs after about 5 minutes of rest in a semi-supine position.
- h. A 12-lead ECG will be performed after resting in a semi-supine position for at least 5 minutes. ECGs will be performed pre-dose. For participants transitioning from ATLAS, the pre-dose Week 48 ECG can also serve as the ATLAS-2M Screening ECG. ECG pre-dose will be performed in triplicate at Day 1. A 2-hour post-dose ECG will also be performed at Days 1 and Week 48 for participants receiving CAB LA + RPV LA with an allowable window of \pm 30 minutes.
- i. Only SAEs related to study participation or to a concomitantly administered ViiV/GSK product will be collected between obtaining informed consent and administration of study drug at Day 1.
- j. On Day 1, the eC-SSRS is to be administered prior to randomization. The eC-SSRS will preferably be completed at the beginning of the visit following administration of other PROs required prior to injections. The eC-SSRS is not required during the Withdrawal visit if withdrawal occurs during the Extension Phase.
- k. Women of childbearing potential only. SR=serum, UR=urine. Pregnancy events will be captured starting at Day 1 following initial exposure to study drug. Serum pregnancy test can substitute for urine pregnancy test if locally required but must be appropriately timed to confirm pregnancy status prior to randomization and first IM administration.
- l. Week 48, Week 96 and Week 152 HIV-1 RNA retest (within 4 weeks) for results $>$ 50 c/mL will be captured as unscheduled visit. Plasma for storage samples will be used for possible future analyses.
- m. A morning specimen is preferred. To assess biomarkers: urine albumin/creatinine ratio; urine protein/creatinine ratio; and urine phosphate. Urine phosphate results from visit 4a are not required by protocol to inform the safety review at visit 4b prior to receipt of initial CAB LA + RPV LA injections.
- n. An overnight fast is preferred; however, a minimum of a 6-hour fast is acceptable.
- o. Only collect if the Withdrawal visit occurs at Week 48, Week 96 or Week 152.
- p. Whole blood/PBMC collection samples may be used for virologic analyses. PBMCs will be collected at baseline Day 1, Week 48, Week 96, Week 152 or Withdrawal if prior to Week 152.
- q. Genetics sample should be collected only for patients who did not participate in the 201585(ATLAS) study (sample was previously collected and stored). Informed consent for genetic research must be obtained before sample collection. Sample may be collected at any visit after signing informed consent, but preferably at the Day 1 visit.
- r. One blood sample for CAB and RPV each to be collected at each PK timepoint. At Day 1, for participant from the ATLAS Q4W arm, PK samples are to be collected pre-dose relative to IM administration. At Week 4B, for participants randomized from SOC, Pre dose PK samples are to be collected: AFTER review of the PK diary to ensure that the samples are taken 20/28 hours after previous oral dose (diaries to be given at Day 1 or W4a); PRIOR to the final oral dose of CAB + RPV; and PRIOR to the first IM injection. At Week 9 and 41, the PK samples should be collected 3 to 10 days after the Week 8 and Week 40 visits, respectively.
- s. Only for Participants entering CAB + RPV Oral Treatment

- t. Participants switching to CAB LA + RPV LA will take final dose of oral lead-in regimen in the clinic at the Week 4B visit and begin injections. If possible, injections should be spaced approximately 2 cm from one another and from the site of any previous injection and or any injection site reaction. Bring RPV LA to approximately room temperature prior to injecting. Time and location of injection (right or left) as well as needle length used will be collected in the eCRF. The first injection can be performed as soon as central lab results become available and safety parameters are reviewed.
- u. All Patient Report Questionnaires/Surveys will be administered via paper instrument at the beginning of the visit before any other assessments are conducted and prior to administration of the eC-CSSRS. Conduct questionnaires/surveys upon Withdrawal only if occurring at or prior to Week 48
- v. The HIVTSQc is to be administered to all participants transitioning from ATLAS and new participants transitioning from oral SOC. For participants transitioning from ATLAS, the version of the HIV-TSQc instrument to be administered will be based on the initial randomization arm at ATLAS Day 1
- w. For patients randomized to oral SOC at Day 1 in ATLAS or new patients on SOC, the reasons for willingness to switch ART will be assessed at Day 1. For patients randomized to CAB LA + RPV LA Q4W in ATLAS, the reasons for willingness to continue long-acting ART in ATLAS-2M will be assessed at Day 1.
- x. Preference Questionnaire will be administered to all participants
- y. Refer to Section 5.5 of the protocol for additional information on performing withdrawal assessments. HIV-1 RNA will be collected as Storage sample only if withdrawal assessments coincide with Week 52 or Week 100 (as per Section 5.5)
- z. Participants receiving one or more injections with CAB LA and/or RPV LA will be assessed with clinic visits at months 3, 6, 9 and 12 during the Long-Term Follow-Up Phase
- aa. Preference at Week 152 will be administered only to participants who received oral bridging during the Maintenance and/or Extension Phases

Note: BP – Blood pressure, HR – Heart Rate, HDL – High Density Lipoprotein, LDL – Low Density Lipoprotein, PT Prothrombin Time, PTT Partial Thromboplastin Time, INR International normalized ratio

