| 
 To characterize CAB and RPV concentrations and population pharmacokinetics and identify important determinants of variability | 
 Plasma PK parameters for CAB LA and RPV LA (when evaluable, Ctrough, concentrations post dose [\simCmax], and area under the curve [AUC]) Demographic parameters including, but not limited to, age, sex, race, body weight, body mass index, and relevant laboratory parameters will be evaluated as |

| Objectives | Endpoints |
|---|---|
| | potential predictors of inter- and intra-participant variability for pharmacokinetic parameters |
| 
 To assess preference for CAB LA + RPV LA every 8 weeks or CAB LA + RPV LA every 4 weeks LA compared to oral antiretroviral (ARV) To assess preference for CAB LA+ RPV LA every 8 weeks compared to CAB LA + RPV LA every 4 weeks | 
 Preference for CAB LA + RPV LA every 8 weeks and CAB LA + RPV LA every 4 weeks compared to oral ARV and preference for CAB LA + RPV LA every 8 weeks compared to CAB LA + RPV LA every 4 weeks will be assessed using a preference questionnaire at week 48 (or Withdrawal). |
| 
 To assess patient reported health-related quality of life, treatment satisfaction, injection tolerability, and treatment acceptance. | 
 Change from Baseline (Day 1) in HRQoL at Week 24, and Week 48 (or Withdrawal) Change from baseline (Day 1) in total “treatment satisfaction” score, and individual item scores of the HIV Treatment Satisfaction Status Questionnaire (HIVTSQs) at Week 24, 48 and 152 (or Withdrawal) Change in treatment satisfaction over time using the HIV Treatment Satisfaction Change Questionnaire HIVTSQc at Week 48 (or Withdrawal). Change from Week 8 in Dimension scores (“Bother of ISRs”, “Leg movement”, “Sleep”, and “Injection Acceptance”) and individual item scores assessing pain during injection, anxiety before and after injection, willingness to be injected in the future and overall satisfaction with mode of administration over time will be assessed using the Perception of Injection questionnaire (PIN) at Weeks 24, 48 and 152 (or Withdrawal) Change from Baseline (Day 1) in treatment acceptance at Week 24, Week 48 and 152 (or Withdrawal) will be assessed using the “General acceptance” dimension of the Chronic Treatment Acceptance (ACCEPT) questionnaire |

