12.5.1. Statistical Methodology Specification

| Statistical Analyses |
|--|
| Endpoints |
| 
 • Change from Baseline in 
 ○ HIVTSQs total treatment satisfaction score at Weeks 24,48 and 152 ○ ACCEPT general acceptance score at Weeks 24, 48 and 152 ○ HAT-QoL (Life satisfaction, HIV medications, disclosure worries) at Weeks 24 and 48 • Change from Week 8 in PIN Domain Scores (Bother of ISRs, Leg movement, Sleep, and Acceptance) and Individual Items Scores (Anxiety before, Pain, Satisfaction, Anxiety After, Willingness) at Weeks 24, 48 and 152 |

| Statistical Analyses | |
|---|--|
| Model Specification | |

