| Dataset | |
| 
 LOCF dataset will be used. | |
| Model Results Presentation | |
| 
 Adjusted treatment difference (Q8W – Q4W), its 95% CI and the associated p-value. The interaction between treatment and the baseline score will be included in a footnote. Plots of adjusted mean change from baseline (95% CI) for each treatment group, and the adjusted mean difference (95%CI) between the two treatment arms from the model will be generated across visit. | |

| Statistical Analyses | |
|--|--|
| HIVTSQc | |
| 
 Total Treatment Satisfaction Score (Change) at Week 48 | |

| |
|--|
| Model Specification |
| 
 • An analysis of variance (ANOVA) model will be used with covariates: treatment, age (<50, \geq 50 years old), prior exposure to CAB+RPV (i.e. 0 weeks, 1 to 24 weeks, $>$24 weeks), sex at birth and race (i.e. white, non-white). • Adjusted point estimates will be derived as LSMEANS using the observed margins (OM) option within PROC MIXED in SAS. • Interactions between treatment and each of the covariates will not be assessed unless the exploratory subgroup analyses on the primary endpoint highlights significant interactions. In this situation, the interaction(s) of interest will be assessed and, if necessary, results will be reported in the clinical study report. If interactions are found to be significant ($p<0.10$), results may be presented separately by subgroup. • No adjustment for multiplicity will be applied as these analyses will be considered supportive. |
| Dataset |
| The observed case (OC) dataset uses only the data that is available at Week 48, with no imputation for missing values. |
| Model Results Presentation |
| Adjusted means, 95% CI, and associated p-value will be presented for the treatment difference (Q8W – Q4W). |

| |
|---|
| Statistical Analyses |
| PIN/HIVTSQs |
| 
 • Change from Week 8 in the PIN acceptance score at Week 24, Week 48 and Week 152 • Change from Sub-study Baseline in the HIVTSQs total treatment satisfaction score at Sub-study Week 16, Sub-study Week 24 (for Q8W arm) or Sub-study Week 20 (for Q4W arm). |
| Statistical Test |

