- o. Only collect if the Withdrawal visit occurs at Week 48, Week 96 or Week 152.
- p. Whole blood/PBMC collection samples may be used for virologic analyses. PBMCs will be collected at baseline Day 1, Week 48, Week 96, Week 152 or Withdrawal if prior to Week 152.
- q. Genetics sample should be collected only for patients who did not participate in the 201585(ATLAS) study (sample was previously collected and stored). Informed consent for genetic research must be obtained before sample collection. Sample may be collected at any visit after signing informed consent, but preferably at the Day 1 visit.
- r. One blood sample for CAB and RPV each to be collected at each PK timepoint. At Day 1, for participants from the ATLAS Q4W arm, PK samples are to be collected pre-dose relative to IM administration. At Week 4B, for participants randomized from SOC, Pre dose PK samples are to be collected: AFTER review of the PK diary to ensure that the samples are taken 20/28 hours after previous oral dose (diaries to be given at *Day 1 or W4a*); PRIOR to the final oral dose of CAB + RPV; PRIOR to the first IM injection.
- s. Only for Participants entering CAB + RPV Oral Treatment
- t. Participants switching to CAB LA + RPV LA will take final dose of oral lead-in regimen in the clinic at the Week 4B visit and begin injections. If possible, injections should be spaced approximately 2 cm from one another and from the site of any previous injection and or any injection site reaction. Bring RPV LA to approximately room temperature prior to injecting. Time and location of injection (right or left) as well as needle length used will be collected in the eCRF. The first injection can be performed as soon as central lab results become available and safety parameters are reviewed.

- u. All Patient Report Questionnaires/Surveys will be administered via paper instrument at the beginning of the visit before any other assessments are conducted and prior to administration of the eC-CSSRS. Conduct questionnaires/surveys at Withdrawal only if occurring at or prior to Week 152.
- v. The HIV-TSQc is to be administered to all participants transitioning from ATLAS and new participants transitioning from oral SOC. For participants transitioning from ATLAS, the version of the HIV-TSQc instrument to be administered will be based on the initial randomization arm at ATLAS Day 1.

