15.3.4. Assessment Window for Health Outcome Data

15.3.4.1. PIN / HAT-QoL / HIVTSQs / HIVTSQc / ACCEPT / Preference in Main Study

PIN, HAT-QoL, HIVTSQs, HIVTSQc, ACCEPT, Preference, reasons for oral bridging and preference questionnaire assessments will be assigned to analysis visits as follows:

1. Baseline will be defined as last available recorded value up to and including the Maintenance treatment start date (expected to be collected at Day 1). Baseline is not applicable for PIN, HIVTSQc and Preference assessments.
2. For post-baseline visits, if the nominal visit identifier as captured in the source dataset corresponds to a scheduled collection per the Time and Events Schedule (see Section 15.2 and Table 15) and the assessment is collected in the Maintenance or Extension Phase (per Table 18), then the nominal visit identifier will be kept as the analysis visit.
3. For post-baseline visits, if the nominal visit identifier is unscheduled or withdrawal, then the following procedure will be used:
 - a) Assign the assessment to a study phase according to Table 18. Proceed to step b if the assessment is assigned to the Maintenance or Extension Phase.
 - b) Identify the 'last nominal visit' with the HO assessment performed prior to the unscheduled/withdrawal visit to be slotted in the same phase.
 - c) The unscheduled/withdrawal visit will be slotted to the planned nominal visit subsequent to the 'last nominal visit' in the same phase. If the 'last nominal visits' does not exist (e.g. no records originate from a planned nominal visit), then the unscheduled/withdrawal visit will be slotted to the first planned nominal visit after Day 1 in the same phase. If the planned nominal visit subsequent to the 'last nominal visit' is not available, then the unscheduled/withdrawal visit will be slotted to the last planned nominal visit after Day 1 in the same phase.

Example 1, for HATQoL, the planned nominal visits are Day 1, Week 24, and 48. If a participant has the 'last nominal visit' (with HATQoL assessment) at Week 24 prior to withdrawal at Week 36, the withdrawal assessment will be slotted to the subsequent planned nominal visit of Week 48.

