15.7.2.2. Handling of Missing data for Statistical Analysis

| Element | Reporting Detail |
|------------|---|
| Snapshot | 
 In the Snapshot dataset, participants without HIV-1 RNA data in the assessment window for the visit of interest (due to missing data or discontinuation of IP prior to the visit window) do not belong to 'HIV-1 RNA < 50 c/mL (or <200 c/mL)'. The nature of this missing data will be further classified in Snapshot summaries as either 'HIV-1 RNA ≥ 50 c/mL' (or "HIV-1 RNA ≥ 200 c/mL") or 'No Virologic Data at Week X'; Appendix 9: Snapshot Algorithm Details for full details |
| LOCF | 
 In the LOCF dataset, missing values will be carried forward from the previous, non-missing available on-treatment assessment. If the baseline value is missing any missing values until the first non-missing value will remain missing. |

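### Withdrawal questionnaires stop at Week 48 in the Q8W schedule but at Week 152 in the Q4W schedule, so the supportive Week 152 patient-reported comparisons treat withdrawals unequally by arm, by an unknown amount and in an unknown direction

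*SAP*

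**What the plan says.** The two main-study schedules set different limits in the same footnote, u. For Q8W (SAP 15.2.2) it is "Conduct questionnaires/surveys upon Withdrawal only if occurring at or prior to Week 48". For Q4W (15.2.1) it is "Conduct questionnaires/surveys at Withdrawal only if occurring at or prior to Week 152".

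The endpoint table in 2.2 makes no distinction by arm. It times the satisfaction endpoint as "HIV Treatment Satisfaction Status Questionnaire (HIVTSQs) at Week 24, 48 and 152 (or Withdrawal", and gives the same timing for PIN and ACCEPT. Both schedules mark HIVTSQs, ACCEPT and PIN at Week 152 and at withdrawal.

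Section 12.5.1 models "HIVTSQs total treatment satisfaction score at Weeks 24,48 and 152" by ANCOVA as Q8W minus Q4W, and does the same for ACCEPT and PIN. For these models, "LOCF dataset will be used". Under 15.7.2.2, "missing values will be carried forward from the previous, non-missing available on-treatment assessment".

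**The concern.** Whether a withdrawal score exists between Week 48 and Week 152 depends, on the text as written, on the randomised arm. LOCF then fills the gap in one arm with a score from the time of leaving and in the other with an older one. Covariate adjustment does not repair a difference in what was collected, and no planned analysis addresses it. The affected results are secondary endpoints in an open-label trial. The Q8W footnote also contradicts the SAP's own endpoint table, so the programmer and the sites have two instructions to choose from.

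**Working it through.** The SAP states no figure here to reproduce. The check is to follow the rules for comparable participants and then see what the result could be worth.

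**Extension Phase withdrawal (for example, at Week 120).** Both participants have planned scores up to Week 48.

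- Q4W: footnote u requires the form. If it falls in the on-treatment window of 15.4.2 (35 days from the last injection, or one day after the last oral dose if later), it is usable. The participant has no earlier planned record in this phase, and 15.3.4.1 says "then the unscheduled/withdrawal visit will be slotted to the first planned nominal visit after Day 1 in the same phase". Table 15 makes that Week 152. The withdrawal score becomes the Week 152 value.
- Q8W: footnote u excludes the form. Week 152 is missing, and LOCF carries forward the last on-treatment score, normally Week 48.

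The handling differs by arm.

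**Maintenance Phase withdrawal after Week 48 (for example, at Week 70).**

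- Q4W: no later planned visit exists in that phase, so 15.3.4.1 slots the form back to Week 48. The planned Week 48 record takes precedence for summaries (15.3.6). The same section says that all valid assessments feed algorithms with rules of their own, and names LOCF. Whether LOCF carries the withdrawal score or the planned Week 48 score to Week 152 is therefore not settled.
- Q8W: there is no form, and the Week 48 score is carried forward.

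The arms differ here only if LOCF takes the withdrawal record.

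**Not affected.** Week 24 and Week 48 comparisons, because both schedules collect withdrawal forms up to Week 48. HAT-QoL and HIVTSQc have no planned Week 152 visit.

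**Illustration of size, HIVTSQs total (0 to 66, SAP 15.6.6).** Let p be the share of Q8W participants whose post-Week 48 withdrawal score is not collected but would have been used. Let d be their mean withdrawal score minus the score carried forward. Collecting the scores would change the Q8W mean by p × d. Omitting them therefore shifts Q8W minus Q4W by -p × d, ignoring covariate adjustment. Neither p nor d is in the SAP; both are assumed.

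| p | d = -20 | d = -10 | d = 0 | d = +5 |
|---|---|---|---|---|
| 2% | +0.4 | +0.2 | 0 | -0.10 |
| 5% | +1.0 | +0.5 | 0 | -0.25 |
| 10% | +2.0 | +1.0 | 0 | -0.50 |
| 15% | +3.0 | +1.5 | 0 | -0.75 |

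Positive values favour Q8W. For example, -0.15 × (-20) = +3.0 and -0.15 × 5 = -0.75. Because 12.5.1 fits the HIVTSQs and ACCEPT models separately for participants with and without prior CAB+RPV exposure, p is the share within each exposure group, not of the whole arm. With the same limit in both arms, the shift from this source is 0 for any p and d.

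**The case against.** The strongest reply is that this is unrevised text, not a chosen asymmetry. Other Q8W footnotes (l, o, p and aa) already refer to Week 152. Footnote y shows the same kind of lag: the Q4W version lists Week 156 and the Q8W version does not. Nothing shows that sites collected differently. This is a fair reading, but it remains an inference, and it explains the contradiction without removing it. Nor does it help that the schedule is reproduced from the protocol: the SAP flags a schedule typo in 15.2.3 and leaves this one standing.

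The stakes are also limited. The type I error-controlled HIVTSQs test is at Week 48, and 12.5.1 treats the other tests as supportive. LOCF uses on-treatment values only, so late Q4W forms drop out too. Both points stand and narrow the issue.

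A reader might infer that the rule biases Week 152 in favour of Q8W, on the ground that people who leave are less satisfied than they were at Week 48. Assuming 5 to 15% withdrawing and falls of 5 to 15 points would give 0.05 × 5 = 0.25 to 0.15 × 15 = 2.25 points towards Q8W. The SAP does not support this. That range admits only falls, so its sign is built in. The SAP also provides for participants who move to marketed product or alternative HAART for reasons unrelated to safety, and they need not be dissatisfied.

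**Conclusion.** The inconsistency is real. Q8W footnote u conflicts with the Q4W footnote and with the arm-neutral endpoints. Followed as written, it makes the Week 152 HIVTSQs, ACCEPT and PIN comparisons handle withdrawals unequally. This is certain for on-treatment Extension Phase withdrawals before Week 152. For Maintenance Phase withdrawals after Week 48 it depends on which record LOCF uses.

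Size and direction are unknown. The shift favours Q8W only if scores worsen between Week 48 and withdrawal; it is zero if they do not change and goes against Q8W if they improve. The range of -0.75 to +3.0 HIVTSQs points rests wholly on the assumed p and d. The SAP alone does not show that collection differed in practice.

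**What to change.** Reconcile Q8W footnote u with the Q4W footnote and the 2.2 endpoints, so that it carries the same Week 152 limit. Because 15.2.2 reproduces the protocol's schedule, check the protocol's own wording at the same time. Editing the SAP copy does not change what sites collected, and with this amendment covering a sub-study entered after at least 152 weeks, it may come too late to recover forms.

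If collection did differ by arm, disclose it and keep the as-collected analysis. Alongside it, add a Week 152 sensitivity ANCOVA that excludes post-Week 48 withdrawal questionnaires in both arms, both as slotted Week 152 values and as values LOCF may carry forward. Run it within each prior-exposure group for HIVTSQs and ACCEPT, and with the planned model for PIN. State which record LOCF uses for Maintenance Phase withdrawals after Week 48.

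The cost is one footnote, one clarifying sentence and, if needed, one extra analysis. As a sensitivity analysis it sets aside valid Q4W withdrawal forms only there.
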